In order to develop therapeutic taVNS for psychiatric problems, a necessary first step is to establish the appropriate parameters that will modulate cognitive and affective responses among healthy participants. We will first recruit 45 healthy participants (randomized to 9 different dose durations) to determine the dose-response curve for taVNS on a range of vagally-mediated physiological measures and subjective mood. At a single session, heart rate variability (HRV), skin conductance (SC), and electroencephalography (EEG) will be measured at baseline, concurrently with stimulation, during learning and cognitive tasks and finally during a recovery period. Utilizing rest, learning and recovery conditions concurrent with multiple physiological measures we will demonstrate whether there is process- or physiological modality-specific modulation or co-activation across domains and measures. Our team of experts in brain stimulation, neuroscience, and psychophysiology are uniquely suited to accomplish these tasks. After establishing the dose-response curve, the findings of our dosing may be evaluated an additional sample of 45 participants seeking treatment for anxiety or trauma related disorder.

An additional goal of this study is to evaluate invasive vagus nerve stimulation (VNS) to determine how taVNS relates to other established forms of brain stimulation via the vagus nerve. VNS is currently FDA approved for depression and epilepsy, and research has indicated that patients also report decreased anxiety symptoms. Therefore, patients with previously implanted VNS, will be invited to complete this study. They will be administered similar tasks as participants who receive taVNS, and a full psychophysiological profile will be assessed. This study will only recruit individuals who currently have implanted VNS, given the invasive procedure. Although VNS is FDA approved, nearly 150,000 patients have received VNS worldwide over the past 25 years. Therefore, limited patients in the study area have received VNS, so this study expects to recruit <5 patients for this study goal.

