**Aim 1. Establish the dose-response curve secondary to transauricular vagus nerve stimulation (taVNS) for vagally-mediated physiological indicators at rest.** We hypothesize that a dose-response curve will be observed with higher doses than typically administered in taVNS protocols being more efficacious in affecting physiological responding. Exploratory Aim 1a. Examine whether dose-response curves vary as a function of physiological measure (e.g., EEG/HRV, etc.). Exploratory Aim 1b. Examine whether a dose-response curve emerges for state measures of mood and interoceptive sensitivity.

**Aim 2. Establish the dose-response curve secondary to transauricular vagus nerve stimulation (taVNS) for vagally-mediated physiological indicators during fear and cognitive challenge.** We hypothesize that higher doses than typically administered in taVNS protocols will be more efficacious in affecting physiological responding and performance. Exploratory Aim 2a. Examine whether dose-response curves vary as a function of different physiological measures. Exploratory Aim 2b. Examine whether a dose-response curve emerges for cognitive and/or fear learning performance.

**Aim 3. Assess tolerability and feasibility among a sample of participants with anxiety and trauma related symptoms.** We hypothesize that utilizing taVNS among participants with anxiety and trauma symptoms will be well tolerated and will modulate autonomic arousal and fear processes, as indicated in physiological indicators.

**Exploratory Aim 3.** Examine whether invasive VNS and taVNS result in similar modulation of physiological measure (e.g., EEG/HRV, etc.), state measures of mood and interoceptive sensitivity, and across similar cognitive and affective tasks.

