EEG will be measured using a 32-channel BrainVision actiCHamp system. Data will be processed with BrainVision Analyzer software. Resting EEG will be measured pre-, post-, and concurrently with stimulation, and will be explored for taVNS dose dependent modulation in frequency bands and coherence of the **EEG power spectrum**. For data collected during the learning/attention task, multiple **event-related potentials** (ERPs) and **steady-state visually evoked potentials** (ssVEPs) will be assessed. A variety of ERPs indicative of attention (i.e., orienting, discrimination) will be evaluated across a variety of contexts after stimulation, including fear learning and extinction, and learning more broadly. Some studies have shown taVNS linked enhancements in the P300, an orienting response (Warren et al., 2020), whereas other studies have not (Warran et al., 2019; Keute et al., 2019). A recent evaluation found taVNS related ERP modulations indicative of enhanced cognitive control (i.e., N2; Pihlaja et al., 2020), which is typically increased during engagement of attention and is enhanced during cognitive conflict. Enhancements in the N2 are typically seen across internalizing disorders, and our previous work demonstrates that the N2 is modulated under internal and external threat (Taylor et al., 2020; Moran, Taylor, & Moser, 2012; White, Grant, Taylor et al., 2018). In addition, ssVEPs which are collected by flickering visual stimuli, may be assessed during stimulation. These potentials are modulated by attentional and motivational factors and will provide real-time dose-dependent data regarding taVNS related modulations in attention. Given the extant and emerging literature on the effects of taVNS on brain activity, these ERPs and other relevant ERPs will be explored.

Participants will complete subjective measures of anxiety and depression and related difficulties as well as Self-Reported Units of Distress (SUDs) during stimulation and the tasks and acceptability/tolerability measures (see Section 10.0 Study Design/Methods for surveys and other measures).

The above measures will also be assessed for participants with implanted invasive VNS and then subsequently with noninvasive taVNS.

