After all electrodes are attached, a 1) baseline (5-10 min) physiology measurement will be taken. Then stimulation will begin. See additional information in Section 3.0 (Intervention to be Studied). Participants in the taVNS group (not having implanted VNS) will be randomized to one of 9 doses with 5 participants per dose, increasing in 10 minute increments of active stimulation. All active sessions per dose will be delivered contiguously and at the end of the stimulation period, and sham stimulation at the beginning. This is to ensure that all participants have the same lapse of time between pre- and post-stimulation recording. That is, if a participant is randomized to 60 minutes of active stimulation, the first 30 minutes would be sham stimulation.

For participants with previously implanted vagus nerve stimulation devices, stimulation will be delivered for 30 minutes. They will subsequently be invited to revisit the lab to receive non-invasive taVNS delivered in a comparable manner to the healthy subjects for 30 minutes.

Additional physiology measurements will be taken 2) concurrent with stimulation and during a final recovery measurement (5-10 mins) after stimulation has concluded.

During the base, recovery, and during 3 time points during the 90-minute stimulation period (i.e., 30 minutes, 60 minutes, and 90 minutes), a Passive Auditory Oddball Task will be administered. During this task a relaxing movie (i.e., silent sand art film) is presented concurrent with standard and deviant tones; MMN task from the ERP Compendium of Open Resources and Experiments - ERP CORE; Kappenman et al., 2020; Eriksen & Eriksen 1974).

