## 12.0 Data Management

Power: Dose-response studies are not powered in the traditional manner. To resolve the shape of the continuous dose response function, it is statistically more efficient to select more doses as opposed to more participants (O’Quigley & Conaway, 2010; Kuljus et al., 2006). The number of observations within each dose primarily accounts for sampling variability, which could be achieved with 2-3 observations. Capturing variability is essential to the planned analyses, which underweight the points of greatest variability in estimating the response curve. Thus, the sample size of  $N = 45$  was determined sufficient to accomplish Aim 1 to establish a dose-response curve. Of note, [name] is running three funded projects with these dose-response techniques in optimizing repetitive transcranial magnetic stimulation (rTMS). An additional, sample of 45 participants are included in the case of data loss and to replicate dose-response findings/assess feasibility/tolerability on participants with anxiety or trauma related disorder or symptoms.

Analyses: The psychophysiological data will be processed using standard protocols which have previously been used in this lab and in various other studies (Sege et al., 2017, 2018, Taylor et al., 2020; Grant et al., 2015), and according to published guidelines (Blumenthal et al., 2005; Boucsein et al., 2012; Gatchel et al., 1973; Keil et al., 2014).

Dose-response relationships will be assessed using the multiple comparisons procedure with modeling (MCP-Mod) approach pre- to post-stimulation changes in physiology and behavior. To determine the reliability of a dose response, MCP-Mod fits a set of pre-specified candidate dose-response curves to the data using a multiple-comparisons technique. The pre-specified dose-response curves to be tested would be Emax, logistic, and linear. Significant curves would then be used to develop inferences on optimal doses for a follow-up adaptive-dosing design, with doses more finely resolved around the probable point of maximal efficacy as determined in this project.

**Confidentiality and Quality Control:** All study personnel will complete Social-Behavioral-Educational research CITI training, and also complete in-lab training regarding data security practices. Study personnel will be trained in the IRB protocol. The investigator, and co-investigators will be available to monitor data collection to ensure quality, confidentiality, and adherence to the IRB protocol.

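### MCP-Mod is defined only on pre- to post-stimulation change, but no fear-learning or performance task has a described pre-stimulation run, so Aim 2b and the fear part of Aim 2 lack a workable dose-response outcome

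*Combined protocol and SAP*

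**What the plan says.** The Analyses paragraph of Section 12.0 applies the MCP-Mod "approach pre- to post-stimulation changes in physiology and behavior". It names the candidate shapes ("The pre-specified dose-response curves to be tested would be Emax, logistic, and linear") but no other response variable, and Aim 2 has no analysis of its own.

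Section 1.0 sets Aim 2 as a dose-response curve "for vagally-mediated physiological indicators during fear and cognitive challenge". Exploratory Aim 2b is to "Examine whether a dose-response curve emerges for cognitive and/or fear learning performance". For the 45 healthy participants, the same section says physiology "will be measured at baseline, concurrently with stimulation, during learning and cognitive tasks and finally during a recovery period". Section 4.0 says that event-related potentials "will be evaluated across a variety of contexts after stimulation, including fear learning and extinction, and learning more broadly".

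Section 10.0 describes two recordings before stimulation. One is resting: a "baseline (5-10 min) physiology measurement will be taken. Then stimulation will begin". The other is the oddball, given while a silent film plays, and the sentence that schedules it begins: "During the base, recovery, and during 3 time points during the 90-minute stimulation period (i.e., 30 minutes, 60 minutes, and 90 minutes), a Passive". Section 10.0 then introduces visual search, cued picture viewing and fear learning in a paragraph that opens with the implanted-VNS participants. Its later risk paragraph on tasks again links the fear task to that group.

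**The concern.** A change score needs the same measure on both sides of the intervention. Because the rule covers behavior as well as physiology, it is evidently meant to reach task performance. For the tasks that define Aim 2b and the fear part of Aim 2, however, the schedule supplies no value before stimulation.

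Aim 2 is one of the two dose-response aims, and Section 12.0 uses significant curves to choose doses for follow-up work. If the response for these measures is not settled in advance, it will be chosen after the data are seen: raw task value, task minus rest, or some within-task contrast. With 5 participants per dose, different choices could favour different curves.

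**Working it through.** **Step 1: match each measure to its recordings.**

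| Measure | Before stimulation | During or after stimulation | Described for | Change score computable in dose groups? |
|---|---|---|---|---|
| Resting physiology | Yes, 5-10 min baseline | During stimulation and at recovery | All participants | Yes |
| Passive oddball | Yes, at baseline | 30, 60 and 90 min, and recovery | Dose groups and implanted VNS | Yes for physiology and ERPs; no performance score |
| Fear learning and extinction | None described | After stimulation (Section 4.0) | Implanted VNS in Section 10.0; dose-response study in Sections 1.0 and 4.0 | No |
| Visual search | None described | Within the task period | Implanted VNS (Section 10.0) | No |
| Cued picture viewing | None described | Within the task period | Implanted VNS (Section 10.0) | No |

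**Step 2: consider both readings of who performs the tasks.**

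- *The dose groups do perform them (Sections 1.0 and 4.0).* The nine groups of 5 (9 × 5 = 45) have a post-stimulation value but no pre value. Aim 2b cannot be computed under the rule. For fear-task physiology, the only earlier value is rest, which is a different condition.
- *Only implanted-VNS participants perform them (Section 10.0).* The dose groups then have neither value. The implanted group numbers 5 in Section 6.0 (fewer than 5 in Section 1.0), receives a single 30-minute duration and is not randomized to dose. It cannot support a dose-response curve. Its no-stimulation visit is a within-person control, not a pre value.

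Under either reading, the stated analysis does not yield Aim 2b or a matched change for the fear part of Aim 2.

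**Step 3: what subtracting rest would cost for task physiology.** This applies only if the dose groups perform the tasks. Assume equal variances, scaled to 1, for the resting value X and the task value Y, with correlation r. The documents give no r, so a range is shown.

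- Variance of the difference Y − X: 2(1 − r)
- Residual variance of Y with X as covariate: 1 − r²
- Ratio: 2(1 − r) / (1 − r²) = 2 / (1 + r)

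| Assumed r | Subtraction | Covariate | Ratio | Extra variance |
|---|---|---|---|---|
| 0.3 | 1.40 | 0.91 | 1.54 | 54% |
| 0.5 | 1.00 | 0.75 | 1.33 | 33% |
| 0.7 | 0.60 | 0.51 | 1.18 | 18% |
| 0.8 | 0.40 | 0.36 | 1.11 | 11% |

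The ratio exceeds 1 for every r below 1. Below r = 0.5, subtraction is also worse than ignoring the baseline, because 2(1 − r) is then greater than 1. The formulas leave out the small cost of estimating the covariate slope.

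The plan states no power figure for Aim 2, so there is none to reproduce.

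**The case against.** Several points on the other side stand.

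- A reader might infer that every cognitive task lacks a baseline. That is not so. The passive oddball is run before stimulation, and it is the only task that Section 10.0 explicitly assigns to the dose groups. Its change in physiology or ERPs can be analysed as planned. The plan does not say whether it counts as cognitive challenge.
- A reader might infer that task minus rest biases the dose comparison by mixing task reactivity with stimulation. It does not. If all randomized groups do the same task, average reactivity shifts them equally and cancels in dose contrasts. What remains is lost precision, and its size depends on an unstated correlation. Section 12.0 does not actually say that task minus rest would be used; it is simply the only difference available.
- A reader might conclude from Section 10.0 that the dose groups certainly do not perform the fear task. Sections 1.0 and 4.0 point the other way, so the documents leave this unresolved.
- Aim 2b is labelled exploratory, the sample size is justified for Aim 1, and Section 16.0 calls the work a pilot project. This limits the consequence, but it does not supply the missing outcome.

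It could also be said that a baseline run of the fear task might be added. The documents describe none and do not discuss whether repeating it would be valid, so the point does not depend on this.

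**Conclusion.** The concern holds in this limited form. The only stated response cannot be computed for Aim 2b, and it has no matched pre value for the fear component of Aim 2. This follows from the schedule and needs no numerical assumption. Aim 1, and the oddball's physiological response, are unaffected.

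The disagreement over who performs the tasks matters more than the choice of response, because it decides whether the dose groups have any task data at all. The variance penalty of 54% to 11% is secondary. It assumes equal variances and r between 0.3 and 0.8, and it concerns efficiency, not bias. The plan should be corrected before any task data are examined.

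**What to change.** 1. Reconcile the overview and aims in Section 1.0 and the endpoints in Section 4.0 with the procedures and task-risk paragraph in Section 10.0, and state whether the nine dose groups perform fear learning, visual search and picture viewing. If they do not, state that the fear component of Aim 2 and Aim 2b cannot be addressed by the dose-response analysis.
2. If they do, name the response for each measure in Section 12.0:
   - resting physiology and oddball: the change score, as now;
   - task physiology: the post-stimulation task value, with the participant's resting baseline of the same measure as covariate;
   - task performance: the post-stimulation value, with no subtraction.
3. Do not adjust extinction for end-of-acquisition level in the main analysis. That level is measured after randomization and stimulation, so adjusting for it could remove or distort part of the dose effect.

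Randomization to dose supports comparing post-stimulation values. The cost is a few sentences and, if the dose groups already perform the tasks, no new data collection. The downside is that performance curves rest on between-person differences only, which is already true of the data as scheduled.

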Participants will be randomized to one of 9 dose durations with 5 participants per dose, increasing in 10 minute increments of active stimulation, ranging between 10 and 90 minutes of stimulation. All active sessions per dose will be delivered contiguously and at the end of the stimulation period, and sham stimulation at the beginning. This is to ensure that all participants have the same lapse of time between pre- and post-stimulation recording. That is, if a participant is randomized to 60 minutes of active stimulation, the first 30 minutes would be sham stimulation. After establishing the optimal dose-duration a sample of treatment seeking individuals will be recruited. This dose will be administered to individuals with anxiety and trauma symptoms to ensure that effects are sustained and to determine feasibility and tolerability.

An additional group of individuals with implanted VNS also will be evaluated after 30 minutes of stimulation. Patients at MUSC who participated in the Microtransponder Vivistim trial or other research/treatments involving VNS will be recruited to complete similar cognitive and affective tasks while psychophysiological responses are measured across 3 sessions: control (no stimulation), implanted VNS, and noninvasive taVNS. This will serve as a comparator for whether taVNS is activating similar brain and physiological regions as invasive forms of vagus nerve stimulation. This will also indicate whether mechanisms of taVNS and VNS are comparable. In order to truly determine comparability of these two forms of VNS, it is imperative to assess within subject brain, body, cognitive, and emotional responding across both implanted and non-invasive VNS.

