## 4.0 Study Endpoints

The following indices will be measured to assess modulation of resting and cognitive/emotional challenge via taVNS dose. Each will be processed and scored according to published guidelines (Blumenthal et al., 2005; Boucsein et al., 2012; Gatchel et al., 1973; Keil et al., 2014). Biopac equipment will be used to continuously measure **heart rate/ variability (HRV)** and **skin conductance (SC)** to assess autonomic responses. SC increases are indicative of a sympathetically mediated orienting response (Dawson et al., 2011; Bradley, 2009). Previous studies evaluating taVNS have employed the SC within the context of fear extinction, but have not demonstrated an effect (Burger et al., 2016; 2017), though faster rates of extinction were shown. HR deceleration also is indicative of the orienting response, while higher HR variability is indicative of regulated emotional responding (Appelhans & Luecken, 2006; Bradley, 2009). Decelerations in HR after taVNS have been demonstrated under certain parameters (Badran et al., 2018b). **Pupillometry**

will be assessed to determine anxious arousal and defensive responding as a function of taVNS. Pupil dilation will be measured with a Tobii eyetracker. Previous data has shown that taVNS modulates pupil dilation. Thus, this will be used to aid in determining the optimal dose duration of taVNS.

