## **6.0 Number of Subjects**

This study will recruit 90 community individuals who meet the above inclusion and exclusion criteria, 50% of which will be female. Participants ( $n = 45$ ) who are healthy controls will be recruited to establish the dose response curve. Then this dose will be administered to 40 individuals with anxiety and trauma related symptoms. Participants with implanted VNS ( $n = 5$ ) will be recruited for similar procedures.

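### The three planned curves are all monotone, so the plan cannot show a rise and fall between 10 and 90 minutes, and it defines no other target for the optimal duration

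*Combined protocol and SAP*

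**What the plan says.** All references are to the combined protocol and SAP.

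- **Analysis.** Section 12.0 applies MCP-Mod to pre- to post-stimulation changes and fixes the candidate set: "The pre-specified dose-response curves to be tested would be Emax, logistic, and linear". Significant curves then inform optimal doses for a follow-up adaptive design, with "doses more finely resolved around the probable point of maximal efficacy as determined in this project".
- **Doses.** Section 3.0 randomizes participants to nine durations, five per duration, "ranging between 10 and 90 minutes of stimulation" in 10-minute steps. There is no 0-minute arm.
- **Use within this study.** Section 3.0: "After establishing the optimal dose-duration a sample of treatment seeking individuals will be recruited". Section 6.0: "Then this dose will be administered to 40 individuals with anxiety and trauma related symptoms".
- **Hypothesis.** Aim 1 in Section 1.0 expects "higher doses than typically administered in taVNS protocols being more efficacious in affecting physiological responding". No section predicts a fall-off at long durations.
- **Measures.** Section 4.0 opens with "The following indices will be measured to assess modulation of resting and cognitive/emotional challenge via taVNS dose" and lists heart rate variability, skin conductance, pupillometry, EEG power, event-related potentials and steady-state potentials, with no primary. Pupillometry is said to help determine the optimal duration. Exploratory Aim 1a reads "Examine whether dose-response curves vary as a function of physiological measure".

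No section gives a target fraction, a reference dose, a rule for choosing or averaging several significant curves, or a conclusion if no curve is significant.

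**The concern.** The stated aim is to find where efficacy is greatest, but the candidate curves can place that point only at an end of the range. If the true response rises and then falls, two things can go wrong. The test step may miss the effect, or it may be significant and the fitted maximum then falls at an end of the range, past or short of the true peak.

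A plateau-type definition of optimal would avoid the second problem, but the plan does not give one. The choice of definition, of curve and of deciding measure would then be made after the data are seen, with five participants per arm. The resulting duration goes to the second sample and shapes the follow-up design.

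**Working it through.** **Inputs from the plan.** Nine durations (10, 20, ..., 90 minutes), 5 per arm, and three candidate curves. The sample size reproduces: 9 × 5 = 45. The plan gives no alpha, sidedness, SD, effect size or curve guesses, so there is no power figure to reproduce.

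**Inputs assumed.** SD 1; one-sided 0.025; Emax ED50 20; logistic midpoint 50 and slope 10; maximum effect 1.3 SD over the 10-minute arm.

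**1. Shape (no assumptions needed).** The derivatives are:
- linear: the slope, a constant;
- Emax: Emax·ED50/(ED50+d)²;
- logistic: Emax·p(1−p)/δ.

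None changes sign between 10 and 90, so the maximum of any non-flat fit is at 10 or 90. Fitted to noise-free parabolas peaking at 60 or 70 minutes, all three curves have their maximum at 90. For a peak at 40, all three have it at 10.

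**2. Effect kept if 90 minutes is read off.** For a parabola peaking at p, the fraction kept is 1 − ((90−p)/(p−10))².
- p = 50: 1 − (40/40)² = 0%
- p = 60: 1 − (30/50)² = 64%
- p = 70: 1 − (20/60)² = 89%
- p = 80: 1 − (10/70)² = 98%

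**3. A plateau-type target depends on the curve.** Take the duration reaching 80% of the 10-to-90-minute effect, that is, f(d) = f(10) + 0.8·(f(90) − f(10)). For Emax with ED50 20, f(10) = 0.333 and f(90) = 0.818, so f(d) = 0.721 and d = 20 × 0.721/0.279 ≈ 52. The other curves checked give:
- logistic 30/5: 37
- Emax with ED50 5: 41
- logistic 50/10: 63
- linear: 74

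**4. Detection.** Each candidate gives a unit-length contrast c proportional to its centred shape. The statistic is T = Σcᵢȳᵢ/(s/√5) on 9 × 4 = 36 degrees of freedom, and the largest T is compared with a simulated critical value. That value is about 2.22 for the planned set, 2.43 with an umbrella curve guessed to peak at 50 added, and 2.34 with one guessed at 60.

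Hand check for a parabola peaking at 50: the centred shape has length 1.3 × 1.097 = 1.426, so the best attainable mean of T is 1.426 × √5 = 3.19. The linear and logistic contrasts have correlation 0 with this shape and Emax has 0.337, giving 0.337 × 3.19 = 1.07 against 2.22. The matching umbrella contrast gives 3.19 against 2.43.

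| True shape | Planned set | Umbrella guess 50 | Umbrella guess 60 |
|---|---|---|---|
| Parabola, peak 50 | 14% | 78% | 53% |
| Parabola, peak 60 | 58% | 62% | 69% |
| Parabola, peak 70 | 75% | 70% | 76% |
| Parabola, peak 80 | 80% | 74% | 79% |
| Straight sides, peak 50, half lost by 90 | 43% | 54% | 59% |
| Straight sides, peak 50, a quarter lost by 90 | 65% | 63% | 70% |
| Rise to 50, then plateau | 83% | 78% | 83% |
| Linear | 76% | 70% | 73% |

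Repeated simulations agree to within about one point.

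**The case against.** The strongest reply is that a monotone set is what the hypothesis calls for: the plan expects higher doses to do better and predicts no fall-off. The point of greatest efficacy is mentioned for a follow-up design, and Emax or logistic fits can place a plateau dose inside the range. This stands as a defence of the shapes. It does not supply the missing definition of that plateau dose, and Sections 3.0 and 6.0 use the chosen duration within this study.

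Four stronger readings are tempting, and the documents do not support them.

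- **That the plan contradicts its own hypothesis.** It does not. The fault is the mismatch between the curves and the stated target.
- **That the loss to expect is 14% against 78%.** That comparison needs a parabola returning exactly to its 10-minute level at 90, and a guess equal to the true peak. With gentler falls the gap is small or reversed, and for late peaks a guess of 50 lowers detection.
- **That the fitted curves would support anything from 52 to 90 minutes.** No curve has been fitted, and 52 is the 80% point of one assumed Emax curve. Other guesses give other values.
- **That the choice of measure is wholly unaddressed, with a harm that can be sized.** Pupillometry is tied to the choice, Section 12.0 specifies pre- to post-stimulation change, and Aim 1 concerns rest. What is missing is which measure decides if curves differ. Simulated spread between measures sharing one true curve reflects sampling error in small arms, so it does not size this gap.

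**Conclusion.** The point holds as a missing safeguard and an ill-matched target. That a rise and fall inside 10 to 90 minutes cannot be shown by these curves is algebra and rests on no assumed effect. How much this matters depends on a true shape that the documents do not give. It is serious for a symmetric peak near 50 minutes, moderate if about half the effect is lost by 90, and small for late peaks or a plateau. All detection figures rest on the assumed SD, effect, alpha, sidedness and curve guesses.

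The stakes are limited. Section 16.0 calls this a pilot, Section 1.0 says only that the dosing findings may be taken to a further sample, and Aim 3 is mainly about tolerability and feasibility. The changes are still worth making because they are cheap and the duration is carried forward.

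**What to change.** Before data are seen:

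1. **Define the target.** Replace the point of greatest efficacy with a pre-stated quantity. One example is the shortest duration whose predicted effect reaches a stated fraction of the maximum in the tested range, relative to the 10-minute arm, with a confidence interval. State the rule for choosing or averaging significant curves. State that no optimal duration was identified if no curve is significant or if the response falls with duration. As part of this, name the one measure that sets the duration, and say whether pupillometry is that measure or supportive.
2. **Add one umbrella candidate** (quadratic or beta) with a stated peak guess, and recompute the critical value for four contrasts. State alpha, sidedness and the favourable direction of the deciding measure. Present the curve as a safeguard that detects a mid-range peak, and do not claim that it locates late peaks.

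Cost: item 1 is wording and takes no detection power, although a target below the maximum gives up part of the effect by design if the response is still rising at 90 minutes. Item 2 raises the critical value from about 2.22 to 2.43 (guess 50) or 2.34 (guess 60). If the truth is linear, power falls from 76% to 70% or 73%, a loss of about 3 to 7 points before rounding. The loss for late peaks is similar or smaller. Some significant results will show a false interior maximum. No arm, visit or participant is added, and no duration is recommended.
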